Child Eating Behavior. The Child Eating Behavior Questionnaire (CEBQ) will be used at age 24 months to measure parent's perceptions of their child's eating behavior. The CEBQ includes 8 subscales covering 35 items (190), in which the parents respond whether their child demonstrates the behavior described in each item. Response options range from 1 (never) to 5 (always). Mean scores are calculated for each scale with higher mean scores indicating higher expression of that behavior. The CEBQ has acceptable internally reliability and test-retest reliability (191). The CEBQ has not been validated in a Danish context but has been validated in a Swedish context among children aged 1-6 years (192). The questionnaire is translated into Danish by a professional translator, then back translated and checked by the researcher team for cross-cultural adaptation.

Video-recordings of sensitive parenting and sensitive feeding

Video recordings at child ages 24 months are used to examine child and parent behavior as well as parent-child interaction during feeding and play using the Coding Interactive Behavior (CIB) (193)

INFANT HEALTH

to analyze and code, which is described in the following section. Video recordings are analyzed on a subsample of 100 children.

Parenting and parental stress and family impairment at child ages 9-10, 18 and 24 months

The Mother and Baby Interaction Scale, MABISC (at 9-10 months) (194, 195); the Being a Mother, BaM13 (at 18 and 24 months) (196); the Parental Stress Scale, PSS, (197, 198); and the WHO-5 well-being index, WHO-5 (199, 200); all well validated, internationally and in Danish public health settings (109, 168).

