3.7 The effectiveness study (WP 3)

The effectiveness of the VIPP-PUF intervention is measured as a significant reduction in mental health problems (WP 3a) and a healthy weight development at age 24 months (WP 3b) among vulnerable infants, comparing infant who have received the VIPP-PUF intervention to infants, who have received care as usual.

Outcomes

The primary child outcome is child mental health at age 24 months measured by the Strengths and Difficulties Questionnaire, SDQ (178).

INFANT HEALTH

The secondary outcomes measured at child age 24 months include weight-for-length z-scores, body composition, measures of child development (Ages and Stages Questionnaire 3) and of parental well-being, parental stress, and parents' experiences of family impairment (Being a Mother- questionnaire, BaM1 (196); the Parental Stress Scale, PSS, (197, 198); and the WHO-5 well-being index, WHO-5 (199, 200)). Also, parental feeding practices, child eating behavior, parental sensitivity and parent-child interactions during mealtimes will be assessed by the Preschooler and Child Feeding Questionnaires, PFQ and CFQ (188, 189); the Child Eating Behavior Questionnaire, CEBQ (190); and by video recordings coded using the Coding Interactive Behavior, CIB (216).

Intermediate outcomes at child-age 18 months include child mental health and development measured by the Ages and Stages Questionnaire, Social-Emotional 2, ASQ-SE2 (167) and the Child Behavior Checklist, CBCL-version for children aged 1 ½ -5 years (171), which includes information on regulatory problems of eating, sleep, emotions, and behavioral and cognitive functions (42, 46-48).

The intermediate outcomes at age 18 months include measures of sensitive parenting, the Mother and Baby Interaction Scale, MABISC (at 9-10 months) (194, 195); and measures of parents' wellbeing and feeling of competence and relatedness, and parents' experiences of stress, the Parental Stress Scale, PSS, (197, 198) and the WHO-5 well-being index, WHO-5 (199, 200) as well as measures on parental feeding practices, the Preschooler and Child Feeding Questionnaires, PFQ and CFQ (188, 189).

WP 3a: The effectiveness of the intervention on the child' mental health

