4.2 Statistical analyses

Statistical analyses will be carried out according to the intention to treat principle, where the participants are analyzed according to their CAU/intervention recruitment group. For continuous outcomes (including the primary outcome measured as the SDQ total difficulties score), linear mixed models will be fitted to compare the control group receiving care as usual (CAU) and the VIPP-PUF intervention group. For binary outcomes (e.g., border line/abnormal versus normal SDQ score), logistic mixed-effects regression models will be fitted to compare the control and intervention groups. All models include municipality-specific random effects, allowing for the correlation between outcomes of children from the same municipality. Likewise, cluster-specific random effects will be included.

Differences in weight-for-length between intervention and control groups will be evaluated using analysis of covariance (ANCOVA). Associations between weight-for-length z-score and selected risk factors based on their associations with infant behavior and preschool obesity in the published literature will be explored using linear regression. To assess differences in parental feeding practice and infant eating behavior between intervention and control groups, mean scores on the feeding and eating questionnaires subscales are calculated and analyzed using linear mixed models for repeated measurements, including participant-specific random effects. Further, exploratory analyses regarding feeding practices, eating behavior, and weight development will be carried out.

Other prognostic factors identified from the literature *á priori* will be included in analyses. Examples include parents’ education, employment status, household income, ethnicity, parental age, parental mental health problems and marital status (all obtained from national registers) (160); at the child level, sex, birth parameters, weight-for-length z-scores from birth to age 9 months, regulatory problems from ages 2-9 months, and ASQ:SE2 score at 9-10 months; and at the

INFANT HEALTH

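### Section 4.2 assigns 24-month weight-for-length an ANCOVA that conflicts with its own mixed-model rules, and no model in the plan has a recruitment-period term

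*Protocol*

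**What the plan says.** Section 4.2 of the Protocol opens with general rules; the combined protocol and SAP carries the same text. "For continuous outcomes (including the primary outcome measured as the SDQ total difficulties score), linear mixed models will be fitted" to compare the two conditions. "All models include municipality-specific random effects, allowing for the correlation between outcomes of children from the same municipality". "Likewise, cluster-specific random effects will be included".

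The next paragraph takes particular outcomes. For weight: "Differences in weight-for-length between intervention and control groups will be evaluated using analysis of covariance (ANCOVA". It lists no covariates, random effects or time terms. Subscale scores for parental feeding and child eating are to be "analyzed using linear mixed models for repeated measurements, including participant-specific random effects".

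On adjustment, "Other prognostic factors identified from the literature *á priori* will be included in analyses". The examples are family, child and municipality characteristics, among them early weight-for-length z-scores. None is step, period or date.

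Two other places matter. Section 3.7: "The secondary outcomes measured at child age 24 months include weight-for-length z-scores", which is the outcome for secondary hypothesis 1 in Section 2.9. Section 3.3: "The Child Eating Behavior Questionnaire (CEBQ) will be used at age 24 months", whereas PFQ and CFQ are collected at 18 and 24 months; these three instruments serve hypothesis 5.

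**The concern.** An analyst who follows the first paragraph of 4.2 fits a mixed model with municipality effects to weight-for-length. One who follows the second fits a fixed-effects ANCOVA. The plan does not say which prevails, for the first-listed secondary outcome.

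The feeding and eating sentence raises two smaller questions: whether the municipality effect still applies, and how a participant effect could be estimated for a CEBQ subscale with one score per child.

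The larger issue lies under either reading. In this stepped wedge every municipality starts as control and ends as intervention (Section 3.2), and recruitment ran from 16 August 2021 to 31 October 2023 (Section 3.1). Without a period term, any change over time in the children recruited or in their outcomes is attributed in part to VIPP-PUF.

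**Working it through.** **Plan's own figures.** The plan gives no power or precision for weight-for-length, feeding or eating. Its 306 concerns SDQ only. Two-sided, 2 × (1.96 + 0.8416)² × 5.7² / 2² = 127.5 per arm, 255 in total. With ICC 0.001 and m children per cluster the design effect is 1 + (m − 1) × 0.001, and m = 200 gives 255 × 1.199 = 306; m is not stated. For follow-up, 780 × 0.85 × 0.70 = 464, stated as 460. I use 460.

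**Inputs.** From Section 3.2: 16 municipalities in groups of 6, 5 and 5, and Steps 0 to 3. Assumed: equal periods, equal numbers in each municipality-period cell (460/64 = 7.19 children), outcome SD 1, no covariates, no group-level random effect, linear drift, and every ICC other than 0.001.

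**1. Confounding with time.**
- Control cells: 6×1 + 5×2 + 5×3 = 31. Intervention cells: 6×3 + 5×2 + 5×1 = 33.
- Mean step, control: (10×1 + 5×2)/31 = 0.645.
- Mean step, intervention: (6×1 + 11×2 + 16×3)/33 = 2.303.
- Difference: 1.658 steps of a 3-step span, or 0.55 of it.
- Correlation of condition with step: 1.658 × √(31×33)/64 ÷ √1.25 = 0.74.

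**2. Drift bias in plain ANCOVA.** Bias = 1.658 × drift per step. The nominal SE is √(1/222.8 + 1/237.2) = 0.0933.

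| Assumed drift per step (whole trial) | Bias | Type I error |
|---|---|---|
| 0.02 (0.06) SD | 0.03 SD | 6.5% |
| 0.05 (0.15) SD | 0.08 SD | 14% |
| 0.10 (0.30) SD | 0.17 SD | 43% |

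**3. Does a municipality random effect remove it?** With σ² = (1 − ICC)/7.19, τ² = ICC and λ = σ²/(σ² + 4τ²), the bias per unit of drift per step is 26.5/(13.25 + 2.734λ). Here 26.5 and 13.25 are the within-municipality cross-product (condition with step) and sum of squares (condition), and 2.734 is the between-municipality sum of squares. This gives 1.67, 1.72 and 1.85 at ICC 0.001, 0.01 and 0.05. The bias rises slightly, because the random effect shifts weight to the before-after contrast within municipalities.

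**4. Clustering alone, no period term.** The true variance of the unadjusted difference is (1 − ICC) × 0.00870 + ICC × 0.0428, where 0.0428 = 6(3/33 − 1/31)² + 5(2/33 − 2/31)² + 5(1/33 − 3/31)².

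| ICC | True / nominal variance | SE ratio | Type I error |
|---|---|---|---|
| 0.001 (documented, for SDQ) | 1.004 | 1.002 | 5.0% |
| 0.01 (assumed) | 1.04 | 1.02 | 5.5% |
| 0.05 (assumed) | 1.20 | 1.09 | 7.3% |

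**5. Cost of the period-adjusted model.** The Hussey-Hughes variance is 16σ²(σ² + 4τ²) / (115σ² + 285τ²). It gives SE 0.140, 0.145 and 0.154 at ICC 0.001, 0.01 and 0.05, or 1.50, 1.55 and 1.66 times 0.0933.

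**6. CEBQ.** With one score per child on a subscale, the participant variance and the residual variance enter only as their sum and cannot be separated.

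**The case against.** The strongest reply is that the municipality rule covers all models and nothing later withdraws it. The feeding sentence says that participant effects are included, not that they are the only ones, so the natural reading adds them to the municipality effect. That stands. A reader might infer that the plan ignores municipality clustering for weight, feeding and eating, but the documents do not support this. For weight-for-length the ANCOVA label creates a conflict, not a proven omission.

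It is also fair that clustering alone is a small matter, negligible at the only ICC in the documents. Larger figures arise for a model with period terms but no municipality effect (variance ratio 1.10 to 1.50, type I error 6.2 to 10.9% at ICC 0.01 to 0.05). That model is neither planned nor recommended, so those figures do not measure the plan's error.

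Third, the missing period term is not peculiar to these outcomes, and no passage shows drift in standardised z-scores. Both are true. Section 3.1 does describe pandemic disruption and repeated retraining in identifying vulnerable children during recruitment, so the mix of children could have changed. That makes drift plausible; it does not show its size or direction.

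Last, the CEBQ point is one of wording. Dropping the redundant effect leaves the estimate and its SE unchanged.

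**Conclusion.** The point holds as a conflict in the text plus a missing term. ANCOVA for weight-for-length contradicts two rules stated just before it, the feeding and eating sentence leaves the municipality effect unstated, and the CEBQ cannot support a participant effect.

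The consequential gap is the absence of a period term from every model. About 55% of any linear drift across the trial enters a plain ANCOVA estimate, so 0.2 SD of drift would give about 0.11 SD of bias. With a municipality random effect the share is 56 to 62% (1.67/3 to 1.85/3) at ICC 0.001 to 0.05. A reader might infer that extending the SDQ model to weight-for-length is enough. It is not, because that model as written also lacks a period term.

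The results are not shown to be biased; that depends on drift the documents do not quantify. Section 3.1 reports very uneven recruitment between municipalities, so the equal-cell figures are indicative. The direction of the confounding follows from the design itself.

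**What to change.** In Section 4.2:

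- Replace the ANCOVA sentence with a linear mixed model for 24-month weight-for-length z: municipality random effect, fixed effects for recruitment step, and the 9-10-month weight-for-length z as a named covariate.
- For the repeated PFQ and CFQ scores, state the same municipality and step terms plus a participant random effect.
- For the CEBQ, use the municipality and step terms without a participant effect.
- Add fixed step effects to the SDQ model.

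This needs no new data, since municipality and recruitment date are known for each child. The cost is precision: under the equal-cell assumption at N = 460 the SE is 0.140 to 0.154 SD against 0.093 for plain ANCOVA. Intervals about 1.5 to 1.66 times as wide should be acknowledged in the SAP before the analysis is run.

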The role of ethnicity, socioeconomic position of the parents and parental mental health problems will be addressed, using data from National registries or from the Child Health Database, including recorded by CHNs at home visits between ages 0 and 6 months. Specifically, we will explore whether trajectories of feeding and eating behavior and of dysregulation (eating, sleep, and emotional expression) measured between 2 and 9 months (44) and 18 and 24 months will be modified by the intervention, and to what degree eating behavior and dysregulation influences the weight-for-length-z scores at ages 24 months. Also, we will investigate the influences of parental experienced stress and parent-child relational problems at ages 9 month and 18 months on weight-for-length z scores at age 24 months.

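### Section 4.2 does not put the 9-10-month PSS and WHO-5 scores into the models for the 24-month PSS and WHO-5 outcomes

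*Protocol*

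**What the plan says.** **Measurement.** Protocol section 3.3 has a heading "Parenting and parental stress and family impairment at child ages 9-10, 18 and 24 months". Under it stand "the Parental Stress Scale, PSS, (197, 198); and the WHO-5 well-being index, WHO-5 (199, 200); all well validated". In the same sentence MABISC is limited to 9-10 months and BaM13 to 18 and 24 months. PSS and WHO-5 carry no narrower age, so the ages in the heading apply to them. Section 3.7 (WP 3b) supports this for stress, since it plans to study the "influences of parental experienced stress and parent-child relational problems at ages 9 month and 18 months" in relation to weight at 24 months.

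**Role.** Section 3.7 lists among the 24-month secondary outcomes "measures of child development (Ages and Stages Questionnaire 3) and of parental well-being, parental stress", with PSS and WHO-5 named as instruments. They serve secondary hypothesis 3 in section 2.9.

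**Analysis.** For continuous outcomes, section 4.2 says "linear mixed models will be fitted to compare the control group receiving care as usual (CAU) and the VIPP-PUF intervention group", with random effects for municipality and for cluster. A mixed model for repeated measurements with participant-level random effects is described only for the feeding and eating subscales. Further prognostic factors chosen a priori "will be included in analyses. Examples include parents", after which come socio-demographic factors and register-based parental mental health problems. The child-level examples are "sex, birth parameters, weight-for-length z-scores from birth to age 9 months, regulatory problems from ages 2-9 months, and ASQ:SE2 score at 9-10 months". Baseline PSS and WHO-5 do not appear. The Combined protocol and SAP has the same text in its sections 3.3, 3.7 and 4.2.

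**The concern.** When a scale is measured before and after an intervention, its baseline value is usually the most informative single covariate for the later score. The plan names the baseline ASQ:SE2 score but no baseline score for the two parent scales, although the trial collects both and tests both at 24 months. Two things are at stake.

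- **Precision.** A 24-month comparison without the baseline score carries variance that the trial's own data could remove.
- **Pre-specification.** With an open list, whether to adjust PSS and WHO-5 for baseline can be decided after the data are seen. Control families are recruited early in each municipality and intervention families later, and section 3.1 describes recruitment as disrupted and extended. Parental distress at entry could therefore differ between the groups, and the decision to adjust could change the estimate.

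**Working it through.** The plan gives no sample size, power or correlation for PSS or WHO-5, so there is no stated figure to reproduce. The check has two parts.

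**1. Does any analysis text bring in the baseline score?**

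| Text in 4.2 or 3.7 | Covers PSS and WHO-5? | Uses their 9-10-month score? |
|---|---|---|
| General linear mixed model (4.2) | Yes, as continuous outcomes | No own-baseline term; no participant-level random effect |
| Repeated-measures mixed model (4.2) | No, feeding and eating subscales only | Not applicable |
| Example covariates (4.2) | Yes, as an open list | Not named; baseline ASQ:SE2 is named |
| Exploratory analysis of parental well-being from repeated questionnaires (3.7, WP 3a) | Yes, in general terms | No model given |
| Parental stress at 9 months as a predictor (3.7, WP 3b) | Stress only, for the weight outcome | Not for the 24-month parent scales |

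None of the five specifies the own-baseline covariate for these two outcomes.

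**2. What could adjustment be worth?**

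Inputs:
- N = 460 at 24 months (section 4.2, sample size re-calculation).
- Significance level 0.05 and power 80% (same place). Sidedness is not stated; two-sided is assumed.
- Correlation r between the 9-10-month and 24-month scores: not in the documents; assumed 0.3 to 0.6.
- A 1:1 split, with clustering and period effects ignored (a simplification).

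Formulas:
- Residual variance factor = 1 − r².
- Equivalent unadjusted N = 460 / (1 − r²).
- Detectable difference in SD units = (1.960 + 0.842) × √(4/460) × √(1 − r²).

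Without adjustment the detectable difference is 2.802 × 0.0933 = 0.261 SD.

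| Assumed r | 1 − r² | Fall in residual variance | Equivalent N | Detectable difference (SD) | Power at an illustrative 0.25 SD |
|---|---|---|---|---|---|
| none | 1.00 | – | 460 | 0.261 | 76.5% |
| 0.3 | 0.91 | 9% | 505 | 0.249 | 80.2% |
| 0.4 | 0.84 | 16% | 548 | 0.239 | 83.3% |
| 0.5 | 0.75 | 25% | 613 | 0.226 | 87.2% |
| 0.6 | 0.64 | 36% | 719 | 0.209 | 91.8% |

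The comparator in the top row has no covariates at all. The planned models will have some, so the relevant quantity is the squared partial correlation given those covariates. Where they share variance with the baseline score, the gain is smaller than shown, and the table is best read as an upper range. The absolute detectable differences are also optimistic, because a stepped-wedge analysis spends information on clustering and calendar time.

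**The case against.** The strongest objection is that the list in 4.2 is introduced as examples. A reader might infer from it that the plan excludes the baseline scores and that the 24-month comparisons discard them. The documents do not support that: absence from an open list is not exclusion. This part of the objection stands in full. What remains is that the plan does not specify the term.

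A reader might also infer that imbalance in parental distress goes wholly uncorrected. That too is more than the text supports. Parental mental health problems are a named covariate, nurse-recorded parental problems up to 6 months are collected (section 3.3), and baseline ASQ:SE2 is named and is parent-rated. These cover part of the same ground, though none replaces the parent's own score on the outcome scale.

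A third objection concerns timing. In section 3.2 the nurse offers either extended usual care or VIPP-PUF in connection with the 9-10-month visit, and parents join afterwards by answering the web questionnaires. Self-reported stress and well-being could respond to that offer, so the scores are not clean pre-allocation measurements, and adjusting for them could absorb a little of any effect. This stands. It is the reason to report the estimate without the term as well. It also means that leaving these scores out of the model for the parent-rated SDQ is a defensible choice.

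Finally, section 3.7 calls the analysis of parental well-being exploratory. That lowers the stakes but does not remove the two scales from the secondary outcomes.

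**Conclusion.** The point holds as a gap in specification for two secondary outcomes. PSS and WHO-5 have a planned baseline, both are tested at 24 months, and nothing in 4.2 says that the baseline score enters either model. Adding it would be expected to improve precision over the model as written, using data the trial already plans to collect.

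The size cannot be fixed from the documents. At an assumed r of 0.3 to 0.6, residual variance falls by at most about 9% to 36%, equivalent to going from 460 to between 505 and 719 children under the simplifications above, and by less where the listed covariates overlap.

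That WHO-5 is measured at 9-10 months rests on the heading in 3.3 and on the reference to repeated parental questionnaires in 3.7. For PSS, the use of parental stress at 9 months in 3.7 is further support.

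A reader might extend the point to the primary analysis, or to BaM13 and the CIB video coding through baseline MABISC. The documents do not make either omission an error. The SDQ model already names the baseline ASQ:SE2 score. MABISC is a different instrument from BaM13 and CIB, and CIB is coded on only 100 children.

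**What to change.** Add to section 4.2, in both documents: *Each 24-month PSS and WHO-5 model includes the same scale at 9-10 months as a covariate; the estimate without this term is also reported, because the baseline questionnaire is answered after the care offer is known.*

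The cost is one sentence of analysis text and one extra estimate per scale. No new data are needed. A short rule is needed for families with a missing baseline scale, preferably imputation. Few such families are expected, because parents enter the study by answering the questionnaires. The sentence should be fixed before the 24-month parent scales are compared between groups.

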3.3 Measurements

Social and emotional development at ages 9-10, 18 and 24 months

The Ages and Stages Questionnaire, Social-Emotional 2, ASQ:SE 2 (version for children aged 1 to 60 months) (167) is used to measure the child's self-regulation, compliance, communication, and adaptive functioning. It comprises 19 to 33 items rated by parents and includes a box, in which parents can check if the behavior is a concern for them. The ASQ:SE2 is well-validated, and the most commonly used measure of young children's social and emotional development, internationally as well as in Denmark (168-170).

Mental health problems at ages 18 months

The Child Behavior Checklist, CBCL-version for children aged 1 ½ -5 years answered by parents (171) is used to measure problems of eating, sleep, emotional problems, behavioral problems and problems of hyperactivity, concentration, communication, language, and social interaction (42, 46-48, 172-174). The CBCL *1 ½ -5 years* comprises 99 items, including problems of overeating and problems of dysregulation (174). CBCL is predictive of persistent emotional and behavioral dysregulation, including overt symptoms of ADHD (172, 173). It is one of the internationally most used and validated psychometric tools (175), and the version for children aged 1 ½ -5 years has been used in several population-based studies in Denmark (13, 152).

Developmental status at ages 24 months

The Ages and Stages Questionnaire, Third Edition (ASQ-3) (176) is a 30-item measure of child developmental progress. The ASQ-3 consists of the following subscales: communication, gross motor, fine motor, problem-solving, and personal-social. Each developmental area is scored from 0 to 60, and the total score range is 0-300 with higher scores indicating better development.

Cronbach's alpha ranges from 0.67 to 0.81 for the five subscales for the version for children aged 24 months (177).

Mental health problems at ages 24 months

The Strengths and Difficulties Questionnaire (SDQ) is a well-validated tool for assessing the mental health in children aged 2–17 years. This study uses the parent-version of the SDQ including the impact supplement (see also www.sdqinfo.org) (178). The SDQ t is a short and feasible measure consisting of 25 items, in which parents answer questions covering main areas of child mental health within the following subgroups: hyperactivity, emotional problems, behavioral problems,

INFANT HEALTH

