municipality level, e.g., level of social disadvantage. Interaction terms will be included to explore possible differences in intervention effect (on the primary outcome SDQ score only) between gender, pre-defined subgroups based on weight-for-length z-scores 0-9 months, low versus high scores of regulatory problems 2-9 months (0-2 problems versus ≥ 3 problems of eating, sleep or emotional dysregulation); low versus high baseline ASQ:SE2 scores and parental characteristics. Also, additional analyses of effect modification will further explore the effect by different population groups (socio-economic position, family structure, and migration status).

We will use path analysis to explore whether the effect of the intervention on weight-for-length z-score at age 18 and 24 months is mediated through the above-mentioned risk factors for childhood overweight. Using path analysis, we can assess the direct effect of the intervention, corresponding to the proportion not mediated through risk factors for child overweight, and the indirect effects of the intervention, corresponding to the proportion mediated through selected risk factors for childhood overweight. The total effect is the sum of the direct and indirect effects.

(Please see the WP4 protocol, WP 4b (Version January 2022) for further details regarding the statistical analyses of the process evaluation).

Sample size re-calculation

Based on recent research (239), an updated sample size calculation has been carried out for testing the primary outcome (the SDQ total score). The mean SDQ total score at the baseline, in children with ≥ 3 problems, is expected to be 13 (182) and the intervention group is now expected to reduce the mean SDQ total score to 11 (179). Consequently, to detect a difference in the SDQ total score of 2 while assuming a standard deviation of 5.7 (239), a small cluster effect (assuming an intraclass correlation of 0.001 as there are only 3 large clusters involved), and a significance level of 0.05 and with 80% power, we need a total sample size of 306 participants (240) (21). We expect a participation rate of 85% at the baseline and a 30% dropout rate by the 24-month follow-up assessment, leaving a total of 460 children available for assessments of the primary outcomes, conditioned a recruitment of about 780 children at baseline.

5 Ethics

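### Effect modification by baseline ASQ:SE2 is to be tested in low and high groups with no stated cut-off; a continuous interaction would keep more information if modification is roughly linear

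*Protocol*

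**What the plan says.** The effect-modification plan is in section 4.2 (Statistical analyses) of the Protocol, and the combined protocol and SAP repeats it. It opens: "Interaction terms will be included to explore possible differences in intervention effect (on the primary outcome SDQ score only"). The modifiers are then listed. They include sex, "pre-defined subgroups based on weight-for-length z-scores 0-9 months, low versus high scores of regulatory problems 2-9 months", and finally "low versus high baseline ASQ:SE2 scores and parental characteristics".

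The regulatory-problem modifier has its cut in the text: "0-2 problems versus ≥ 3 problems of eating, sleep or emotional dysregulation". ASQ:SE2 has none in either document, and section 4.2 plans no interaction with ASQ:SE2 as a continuous variable.

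Elsewhere ASQ:SE2 is treated as a scale. Section 3.3 says of the questionnaire: "It comprises 19 to 33 items rated by parents". Section 4.2 lists it among the example prognostic factors as a score: "regulatory problems from ages 2-9 months, and ASQ:SE2 score at 9-10 months". That use is covariate adjustment, not effect modification.

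**The concern.** An interaction is estimated much less precisely than a main effect, and nothing in section 4.2 is sized for one. Reducing a graded score to two groups at that point gives up part of the little information available, unless the effect really does change abruptly at the cut. Because the cut is not stated, the result also depends on a choice that the plan leaves open.

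At stake is how well one exploratory analysis can show whether the benefit on the SDQ differs with baseline socio-emotional difficulty. The score will already have been collected, so the lost precision can be recovered by wording alone.

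**Working it through.** **Inputs from section 4.2.** The sample size text is framed as "to detect a difference in the SDQ total score of 2", "assuming a standard deviation of 5.7", with intraclass correlation 0.001, significance level 0.05, 80% power, 306 required and 460 expected at follow-up.

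**Assumptions, because the documents are silent.** Two-sided test; 1:1 allocation; independent observations; 5.7 taken as the residual SD; no stepped-wedge time adjustment; ASQ:SE2 standardised and normal unless stated otherwise; modification linear in the score.

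**The plan's own figure (main effect only).**
- Per arm: 2 × [5.7 × (1.960 + 0.842) / 2]² = 127.5, so 128 per arm and 256 in total.
- Multiply by 1 + (m − 1) × 0.001. The cluster size m is not stated. A result of 306 needs m of about 201 (or about 192 with the t-test version). This is plausible for three large clusters, so 306 is reproducible, though not uniquely.
- Attrition: 780 × 0.85 × 0.70 = 464, against 460 stated.
- No figure is given for any interaction.

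**Information kept by a split.** Relative to a linear term, a two-group split at c keeps corr(X, 1[X > c])². For a normal score with a proportion p on one side of the cut, this is φ(c)² / [p(1 − p)]. At the median it is 2/π = 0.637, a loss of 36.3%, and 460 × 0.637 = 293.

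| Score and cut | Information lost |
|---|---|
| Uniform, median | 25% |
| Normal, median | 36% |
| Normal, 40/60 | 38% |
| Normal, 30/70 | 42% |
| Normal, 20/80 | 51% |
| Right-skewed (gamma, exponential, lognormal), median | 41–52% |
| Same skewed scores, upper third or upper fifth | about 35–40% |
| True step exactly at the cut, any score | none |

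**Power at N = 460.**
- Main effect of 2 points: SE = 2 × 5.7/√460 = 0.53; power 96%.
- Interaction between equal halves: SE = 4 × 5.7/√460 = 1.06. For a 2-point difference, Φ(2/1.063 − 1.960) = Φ(−0.079) = 47%.
- The same modification kept continuous: halves of a normal score differ in mean by 2√(2/π) = 1.596 SD, so the slope is 2/1.596 = 1.253 SDQ points per SD, with SE 0.5315. Φ(1.253/0.5315 − 1.960) = Φ(0.398) = 65%.
- Simulation (5,000 runs): 46% split and 64% continuous. With the same slope and an upper-fifth cut: 37% against 64%.
- For a 1-point difference between halves: 15% split. Continuous, with slope 0.627: Φ(0.627/0.5315 − 1.960) = Φ(−0.78) = 22%.
- Smallest difference between halves detectable with 80% power after a median split: 2.80 × 1.063 = 3.0 SDQ points, larger than the planned main effect.

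At N = 306 the 2-point figures are 34% and 49%. At the 471 children reported as available in October 2024 (Protocol, section 3.1) they are 48% and 66%.

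**The case against.** Several points can fairly be made for the plan.

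- **The analysis is exploratory.** The hypotheses in section 2.9 contain none on effect modification, and no confirmatory conclusion rests on these terms. This stands and limits the weight of the point. A reader might tie these interactions to the declared interest in for whom the intervention works, but that phrase belongs to the process evaluation in section 3.8.
- **The size of the loss is conditional.** The documents give neither the cut nor the distribution of the score. Children enter because they have three or more PUF problems, so a normal baseline score cannot be taken for granted. This stands: 36% is one case within a range. Nor is it a general rule that cuts away from the median lose more. That holds for a normal score, but for the skewed scores tried, the upper-third and upper-fifth cuts lost less than the median cut.
- **A missing cut is not a data-driven cut.** A reader might infer that the threshold will be chosen after the outcomes are seen. The documents do not say so. Section 3.3 cites the instrument's user guide, and whether a standard threshold is intended cannot be judged from the text. What stands is that the wording leaves the choice open.
- **Linearity is itself an assumption.** If the effect changes only at a threshold, the split is the better test. By the same squared correlation, a linear term would then be the one to lose 36% for a normal score with a step at the median. This is the real downside and is why the fix includes a check.
- **The gain is modest.** For a 1-point modification, power moves only from 15% to about 22%, and the test stays weak either way. This is true, but the gain costs no data.

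**Conclusion.** The point holds for ASQ:SE2 as a low-cost improvement to one exploratory analysis. If modification is roughly linear, the planned split gives up about 25% to over 50% of the information, and 36% in the reference case of a normal score cut at the median. For a modification as large as the whole planned effect, this is the difference between about 47% and 65% power at 460 children, under the assumptions listed with the calculation. Nothing is lost if the true modification is a step at the cut.

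The primary treatment comparison and its sample size are not affected.

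It is tempting to extend the criticism to the other modifiers in the same sentence, but the documents do not support that. The regulatory-problem split has its cut stated in advance, and the 2/π figure does not carry over to a problem count. The weight-for-length subgroups are called pre-defined and rest on repeated measurements. Neither their number nor their form is stated, so it cannot be said that a single score is being cut in two.

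**What to change.** In section 4.2, replace the low-versus-high ASQ:SE2 interaction with an intervention-by-ASQ:SE2 interaction using the baseline score as a continuous variable, and name this as the main test for that modifier. Add a check of linearity by a plot or a spline term. Keep low and high groups only to display estimated effects, and state the cut, fixed before outcome data are examined.

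The cost is a change of SAP wording and one extra model check; no new data, visits or children are needed. The price is reliance on approximate linearity, which the check is there to examine. The interaction should still be reported as exploratory, with its confidence interval, since power remains limited with either method.
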